6.2 Dose Modifications for Non-Hematologic Toxicity

The dose reduction guidelines for non-hematologic toxicities are shown in Table 4.

CONFIDENTIAL

Table 4	Carfilzomib Dose Reductions for Grade 3 or 4 Non-Hematologic Toxicities
---------	--

Event	Action to be Taken
Allergic reaction/hypersensitivity Grade 2 – 3 Grade 4	Hold until ≤ Grade 1, reinstitute at full dose. Discontinue
Tumor lysis syndrome	
$(\geq 3 \text{ of following:} \geq 50\% \text{ increase in creatinine,} uric acid, or phosphate; \geq 30\% increase in potassium; \geq 20\% decrease in calcium; or \geq 2-fold increase in LDH$	Hold carfilzomib until all abnormalities in serum chemistries have resolved. Reinstitute at full doses.
Infection Grade 3 or 4	Hold carfilzomib (no more than 3 weeks) until systemic treatment for infection complete. If no neutropenia, restart at full dose. If neutropenic, follow neutropenic instructions (Table 3).
Herpes zoster or simplex of any grade	Hold carfilzomib until lesions are dry. Reinstitute at full dose.
Neuropathy	
Grade 2 treatment emergent neuropathy with pain or Grade 3 neuropathy	Continue to dose. If neuropathy persists for more than two weeks hold carfilzomib until resolved to \leq Grade 2 without pain. Then restart at 1 dose decrement.
Grade 4 neuropathy	Discontinue carfilzomib
Renal Dysfunction	Please refer to Table 5.
Congestive heart failure	Any patient with symptomatic congestive heart failure, whether or not drug related, must have the dose held until resolution or return to baseline, after which treatment may continue at a reduced dose, or the patient may be withdrawn from the study. If no resolution after 2 weeks, the patient will be withdrawn from the study.
Other non-hematologic toxicity assessed as carfilzomib-related \geq Grade 3	Hold dose until toxicity resolves to \leq Grade 1 or baseline. Restart at 1 dose decrement.

a Carfilzomib should be held until toxicity resolves to \leq Grade 1. Patients who develop irreversible Grade 3/4 non-hematologic toxicity, or toxicity that does not resolve to \leq Grade 1 within 3 weeks, should be removed from the study.

b No more than 2 dose reductions of carfilzomib are allowed.

CONFIDENTIAL

STUDY DRUG(S): CARFILZOMIB AMENDMENT 2 DATE: 25 FEBRUARY 2015

Renal Dysfunction	Recommended Action
\geq 0 and < 25% decrease in CrCl over baseline	Based on investigator judgment; no dose modification may be necessary.
\geq 25% and < 50% decrease in CrCl over baseline	Hold carfilzomib dose until CrCl is stable. If attributable to carfilzomib, resume carfilzomib at one dose decrement. If not attributable to carfilzomib, restart at dose used prior to the event.
≥ 50% decrease in CrCl over baseline or CrCl < 15 mL/minute (NCI-CTC Grade 4)	 Hold carfilzomib dose until CrCl improves to < 25% decrease over baseline and CrCl returns to ≥ 15 mL/ minute (if CrCl dropped to < 15 ml/min). If attributable to carfilzomib, resume carfilzomib at one dose decrement. If not attributable to carfilzomib, restart at dose used prior to the event. If dialysis is required, may resume at a maximal dose of 20 mg/m2 and administer the carfilzomib after dialysis.

Table 5Recommended Action for Renal Dysfunction

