8.1.3 Infusion reaction

Infusion reactions associated with IV administration of carfilzomib were characterized by a spectrum of systemic symptoms including fever, chills, arthralgia, myalgia, facial flushing, facial edema, vomiting, weakness, shortness of breath, hypotension, syncope, chest tightness, or angina. These reactions can occur immediately or up to 24 hours after administration. Administration of dexamethasone prior to carfilzomib dosing reduce the incidence and severity of reactions. Inform patients of symptoms and ask them to contact physician if symptoms of an infusion reaction occur. Infusion reactions should be treated as per institutional protocol.

Infusion reactions (e.g., rash, urticaria, erythema, pruritus, bronchospasm, and hypotension) can occur with the agent used in this study. To identify the grade of a reaction, refer to the list below adapted from the General Disorders and Administration Site Conditions section of the NCI CTCAE v 4.03:

- Grade 1: Mild transient reaction; infusion interruption not indicated; intervention not indicated.
- Grade 2: Therapy or infusion interruption indicated but responds promptly to symptomatic treatment (e.g., antihistamines, NSAIDs, narcotics, IV fluids indicated for ≤24 hours).
- Grade 3: Prolonged (e.g., not rapidly responsive to symptomatic mediation and/or brief interruption of infusion); recurrence of symptoms following initial improvement; hospitalization indicated for other clinical sequelae. Note: any infusion that is interrupted and not resumed within the visit will be considered a Grade 3 reaction.
- Grade 4: Life-threatening consequences; urgent intervention indicated.

Minor symptoms such as flushing, skin reactions, dyspnoea, lower back pain, hypotension, or tachycardia may require temporary interruption of the infusion. However, severe reactions, such as hypotension requiring treatment, dyspnoea requiring bronchodilators, angioedema or generalized urticaria may require immediate treatment discontinuation and aggressive symptomatic therapy. Patients who experience a severe reaction should not be re-challenged.

CONFIDENTIAL

STUDY DRUG(S): CARFILZOMIB AMENDMENT 2 DATE: 25 FEBRUARY 2015

Patients who experience an allergic/infusion reaction may be pre-medicated for subsequent cycles per local guidelines and clinical practice.

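### Table 4 restarts full-dose carfilzomib after Grade 3 allergic reactions that Section 8.1.3, when they match its severe examples, bars from re-challenge, and nothing says which governs

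*Combined protocol and SAP*

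**What the plan says.** Section 6.2, Table 4, has a row for allergic reaction/hypersensitivity with two actions. For Grades 2 and 3 it is "Hold until ≤ Grade 1, reinstitute at full dose". For Grade 4 it is discontinuation. The row has no exception for particular manifestations and no premedication requirement. The table's first footnote adds that the toxicity must resolve within 3 weeks.

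Section 8.1.3 deals with infusion reactions. It describes "severe reactions, such as hypotension requiring treatment, dyspnoea requiring bronchodilators, angioedema or generalized urticaria", says of such events that "angioedema or generalized urticaria may require immediate treatment discontinuation and aggressive symptomatic therapy", and closes with "Patients who experience a severe reaction should not be re-challenged". It also allows premedication for later cycles after an allergic/infusion reaction in general.

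Section 8.1.3 prints a four-grade list adapted from CTCAE v4.03. Grade 4 is reserved for life-threatening consequences. The Grade 3 entry carries a note that "any infusion that is interrupted and not resumed within the visit will be considered a Grade 3 reaction". The word severe is explained by examples and is not tied to a grade.

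**The concern.** Table 4 is where a site looks up what to do with the next dose, and Section 8.1.3 is where the protocol states who must not receive one. If the same patient can fall under both, the outcome depends on which page the site opens first. The error that matters is full-dose re-exposure after, for example, angioedema.

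The protocol recognises that such events can be grave without being life-threatening: Section 11.1.2 gives allergic bronchospasm needing intensive treatment as an example of an event that may be serious on medical judgement alone. Table 4 is also more lenient with a Grade 3 allergic reaction (full dose) than with other carfilzomib-related toxicity of Grade 3 or above (one dose decrement).

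**Working it through.** No arithmetic applies. The check is whether one patient can meet both rules, and whether any other text resolves the clash.

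**Step 1: do the two sections cover the same events?** Section 8.1.3 states that "Infusion reactions (e.g., rash, urticaria, erythema, pruritus, bronchospasm, and hypotension) can occur with the agent used in this study". Urticaria and bronchospasm are allergic-type signs, and the section later treats allergic and infusion reactions under one joint term. The scopes overlap. If they were kept apart, a carfilzomib-related Grade 3 infusion reaction would have no row of its own and would fall to the Other row of Table 4, which restarts at one dose decrement. That still contradicts a bar on re-challenge.

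**Step 2: can a reaction be severe and below Grade 4?** On the Section 8.1.3 list, Grade 4 needs life-threatening consequences. The severe examples are defined by sign (angioedema, generalized urticaria) or by need for treatment (hypotension, dyspnoea), not by threat to life. Take angioedema that is not life-threatening but ends the infusion for that visit. The Grade 3 note then applies.

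**Step 3: compare the instructions.** The four cases are chosen to locate the boundary. They say nothing about frequency.

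| Case | Grade on the 8.1.3 list | Table 4 | Section 8.1.3 | Result |
|---|---|---|---|---|
| Angioedema or generalized urticaria, not life-threatening, infusion not resumed that visit | 3 | Full dose | No re-challenge | Conflict |
| Life-threatening reaction | 4 | Discontinue | No re-challenge | Agree |
| Flushing or skin reaction, brief interruption | 2 | Full dose | May be premedicated for later cycles | Agree |
| Hypotension that settles promptly with IV fluids | 2 | Full dose | Fits both the minor and the severe wording | Unclear |

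The last case is unclear for two reasons. Section 8.1.3 says "Minor symptoms such as flushing, skin reactions, dyspnoea, lower back pain, hypotension, or tachycardia may require temporary interruption of the infusion", yet lists hypotension that needs treatment as severe. And its Grade 2 text covers a reaction that "responds promptly to symptomatic treatment (e.g., antihistamines, NSAIDs, narcotics, IV fluids indicated for" up to 24 hours.

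**Step 4: does other text settle the conflict?** Neither section refers to the other. The Table 4 footnotes set only the hold, the 3-week limit and the cap of two dose reductions. Section 5.1.1 requires dexamethasone before every Cycle 1 dose and as needed afterwards. If treatment-related fever, rigors, chills or dyspnoea appears once dexamethasone has been stopped, it should be resumed at 8 mg before later doses. That reaches one of the four severe examples, dyspnoea. It does not name angioedema, urticaria or hypotension, and it governs premedication, not whether the patient may be re-exposed.

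**The case against.** The best defence is that the two texts can be read together. Section 6 says doses may be adjusted according to the tables, and Section 6.2 calls Table 4 guidelines. The re-challenge sentence in Section 8.1.3 can then be taken as the specific rule that qualifies a general row. A careful site can comply with both by following the stricter one. This shows that the conflict can be survived, not that the protocol resolves it: nothing in Table 4 alerts a site to an exception.

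A second defence is that severe means Grade 4. No text says so, and the examples do not require a threat to life. The Grade 3 note does not prove the opposite, because it applies to any infusion not resumed within the visit, whatever the symptoms. It shows only that a reaction of the severe kind can sit at Grade 3.

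A third point stands in part. Using the Section 8.1.3 list to grade Table 4's allergic row is an inference. Section 6 points to CTCAE v4.03 generally, and no sentence assigns that list to that row. The conflict does not depend on this particular list. It needs only that some reaction matching the examples is graded 2 or 3.

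Three stronger readings are tempting and are not supported:

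- A reader might infer that every Grade 3 allergic reaction is in conflict. Severe is described by example, so only reactions that match the description are.
- A reader might infer that Grade 2 reactions are in conflict too. That turns on treated hypotension, which Section 8.1.3 places on both sides of its own line.
- A reader might infer that a patient restarted after Cycle 1 has no premedication cover. The dexamethasone restart rule in Section 5.1.1 supplies some.

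**Conclusion.** The point holds as an internal inconsistency with a direct bearing on patient safety. For a non-life-threatening Grade 3 reaction that matches the Section 8.1.3 examples, Table 4 directs a full-dose restart, Section 8.1.3 directs no re-challenge, and the protocol does not say which prevails.

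Its reach is any patient with such a reaction. The documents give no incidence for these reactions, so no patient count is offered. Nothing here touches the two-stage design or its error rates.

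The conclusion rests on two assumptions: that the allergic row of Table 4 and Section 8.1.3 cover overlapping events, which the joint terminology supports, and that some reactions matching the examples are graded below 4, which the printed grade definitions allow. The position of Grade 2 reactions is left open because the text leaves it open.

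**What to change.** Amend the allergic row of Table 4 along these lines: *Grade 4, or any reaction that is severe as described in Section 8.1.3: discontinue, no re-challenge. Other Grade 2-3: hold to Grade 1 or lower, then restart at full dose.* Cross-reference Section 8.1.3 and Table 4 to each other, and state that Section 8.1.3 governs severe reactions. Ask the clinical team to decide whether hypotension that responds promptly to IV fluids counts as severe, and record the answer in Section 8.1.3.

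The amendment should stop there. Routing all infusion reactions to the allergic row would give full dose to some Grade 3 reactions, such as fever and chills, that can now fall under the Other row and restart one level lower. Writing in an exemption for treated Grade 2 hypotension would permit re-challenge after something Section 8.1.3 lists as severe. Each would loosen existing protection.

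The cost is one table row and a cross-reference, with no added procedures. The downside is that a few patients with severe reactions below Grade 4 stop drug, as Section 8.1.3 already directs.

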5.1 Treatment Plan

5.1.1 Carfilzomib

Patients receiving carfilzomib treatment must be hydrated in Cycle 1, and as needed from Cycle 2 onwards, and pre-treated with dexamethasone as indicated below.

Pre-treatment Hydration and Fluid Monitoring

Intravenous (IV) hydration will be given immediately prior to each dose of carfilzomib during Cycle 1; 250 to 500 mL normal saline or other appropriate IV fluid should be given to reduce the risk of renal toxicity and of tumor lysis syndrome (TLS). An additional 250 mL to 500 mL of IV fluids will be given as needed following carfilzomib administration. If lactate dehydrogenase (LDH) or uric acid is elevated (and/or in patients considered still at risk for TLS) at Cycle 2 Day 1, then the recommended IV hydration should be given additionally before each dose in Cycle 2. The goal of the hydration program is to maintain robust urine output (e.g., ≥ 2 L/day). Patients should be monitored periodically during this period for evidence of fluid overload. After Cycle 2, patients will be hydrated at the Investigator's discretion.

If the patient has a dedicated line for carfilzomib administration, the line must be flushed with a minimum of 20 mL of normal saline prior to and after drug administration.

Pre-treatment Dexamethasone

Dexamethasone (4 mg for the 20 mg/m² carfilzomib dose and 8 mg for the 56 mg/m² carfilzomib dose) PO/IV will be administered prior to all carfilzomib doses during the first cycle and as needed in Cycle 2 and beyond. If treatment-related fever, rigors, chills, and/or dyspnea are observed post any dose of carfilzomib after dexamethasone has been discontinued, dexamethasone (8 mg PO/IV) should be re-started and administered prior to subsequent doses.

TREATMENT SCHEDULE

Carfilzomib 20 mg/m² IV will be administered over 30 minutes (\pm 5 minutes) on Days 1 and 2 of Cycle 1, followed by escalation to 56 mg/m² IV over 30 minutes (\pm 5 minutes) on Days 8, 9, 15, and 16 of Cycle 1. For patients who have adequately tolerated dosing during Cycle 1, carfilzomib 56 mg/m² IV will be administered over 30 minutes (\pm 5 minutes) on Days 1, 2, 8, 9, 15, and 16 of Cycle 2 and beyond. Patients may continue study treatment until intolerable

CONFIDENTIAL

STUDY DRUG(S): CARFILZOMIB AMENDMENT 2 DATE: 25 FEBRUARY 2015

toxicity, confirmed progressive disease (PD), withdrawal of consent, death, or study closure, whichever occurs earliest. The treatment schedule is provided in the table below.

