5.2 Treatment Duration

Patients will be evaluated for toxicity at the start of each cycle. Every 3 cycles, restaging will occur with imaging, laboratory chemistries, and tumor markers as defined in Appendix D. Patients will continue on treatment until progression as defined in Appendix E or intolerance to side effects.

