7. STUDY ASSESSMENTS AND EVALUATIONS

7.1 Overview

All patients should visit the study center on the days specified within this protocol. The complete Schedule of Assessments for this study is shown in Appendix D. The baseline physical examination, medical history, ECOG PS, 12-lead electrocardiogram (ECG), complete blood counts (CBC), differential and platelets, complete metabolic profile (CMP), prothrombin/partial thromboplastin time/international normalization ratio (PT/PTT/INR), and serum pregnancy test should be done \leq 7 days prior to initiation of treatment. If urine pregnancy test is being done, it must be performed within 72 hours of Cycle 1 Day 1. However, if these initial examinations are obtained within 72 hours of Cycle 1 Day 1 they do not have to be repeated on Cycle 1 Day 1. CT scans and LVEF assessment should be performed \leq 28 days prior to initiation of treatment, as should tumor markers, if appropriate.

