7.2 Baseline Study Assessments

The following information will be collected and procedures will be performed for each patient at screening:

• Written informed consent prior to any other study-related procedures

CONFIDENTIAL

STUDY DRUG(S): CARFILZOMIB AMENDMENT 2 DATE: 25 FEBRUARY 2015

- Medical history (including clinical tumor assessment as appropriate)
- Physical examination, measurements of height (first visit), weight,
- Vital signs (resting heart rate, blood pressure [BP], respiratory rate, and oral temperature)
- ECOG performance status (see Appendix A)
- 12-lead electrocardiogram (ECG)
- Echocardiogram (ECHO) with calculated left ventricular ejection fraction (LVEF) (repeat if/when clinically indicated). Multigated acquisition (MUGA) scan is acceptable if ECHO is not available.
- Concomitant medication review
- CBC including hemoglobin, hematocrit, WBC with 3-part differential and platelets
- CMP to include: glucose, blood urea nitrogen (BUN), creatinine, sodium, potassium, chloride, calcium, carbon dioxide (CO₂), ALT, AST, alkaline phosphatase (ALP), total bilirubin, total protein, and albumin.
- PT/PTT/INR
- Fasting serum chromogranin A (overnight fasting required)
- Serum (within 7 days) or urine (within 72 hours) pregnancy test must be done before Cycle 1 Day 1
- CT scans of the chest, abdomen and pelvis ≤28 days prior to initiation of study treatment; CT scan of abdomen and pelvis is preferred, but CT scan of abdomen is acceptable.
- Archival tumor tissue or 10 unstained slides will be obtained if available

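### The tumor lysis rule in Table 4 and the Cycle 2 hydration trigger use LDH, uric acid and phosphate, but no visit schedules any of the three

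*Combined protocol and SAP*

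**What the plan says.** **The TLS rule.** The TLS row of Table 4 (Section 6.2) requires at least three of the following: a rise of 50% or more in creatinine, "uric acid, or phosphate"; a rise of 30% or more in potassium; a fall of 20% or more in calcium; or a "2-fold increase in LDH" or more. The action is "Hold carfilzomib until all abnormalities in serum chemistries have resolved. Reinstitute at full doses". The row does not say what the changes are measured from.

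**The hydration rule.** Under Section 5.1.1, patients "must be hydrated in Cycle 1, and as needed from Cycle 2 onwards". Fluid is recommended before each Cycle 2 dose "If lactate dehydrogenase (LDH) or uric acid is elevated (and/or in patients considered still at risk for TLS) at Cycle 2 Day 1".

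**The schedule.** Section 7.2 itemises the panel: "CMP to include: glucose, blood urea nitrogen (BUN), creatinine, sodium, potassium, chloride, calcium", then carbon dioxide, ALT, AST, alkaline phosphatase, total bilirubin, total protein and albumin. Appendix D, footnote e, lists the same 14 analytes. Section 7.1 states: "The complete Schedule of Assessments for this study is shown in Appendix D". Section 5.2 points to the same place: "restaging will occur with imaging, laboratory chemistries, and tumor markers as defined in Appendix D".

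**The concern.** Two safety rules depend on laboratory values that the protocol does not ask anyone to collect.

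The TLS rule has the larger problem because its criteria are relative. A doubling of LDH can be recognised only against an earlier value. If LDH is first measured when TLS is suspected, the pre-treatment value can no longer be obtained. A patient may then meet the definition without the site being able to show it, and the hold that the TLS row requires has no documented basis.

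The hydration trigger is a smaller problem. It needs only a value on the day, which can be read against the laboratory's normal range. But no Cycle 2 Day 1 test is scheduled, so each site decides whether the named trigger is measured.

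The protocol treats TLS as a risk worth managing. Section 5.1.1 gives TLS as one reason for hydration before every Cycle 1 dose, and Section 5.3.1 allows urate-lowering treatment in patients at high risk.

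**Working it through.** The plan gives no figure to reproduce here. The check sets the analytes that the rules use against the analytes that are scheduled.

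**Step 1. Analytes used and scheduled.**

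| Analyte | Used in | In the CMP (Section 7.2; Appendix D, footnote e) | Elsewhere in Sections 7.2 to 7.6 or Appendix D |
|---|---|---|---|
| Creatinine | Table 4 | Yes | – |
| Potassium | Table 4 | Yes | – |
| Calcium | Table 4 | Yes | – |
| Uric acid | Table 4; Section 5.1.1 | No | No |
| Phosphate | Table 4 | No | No |
| LDH | Table 4; Section 5.1.1 | No | No |

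The other scheduled laboratory tests are blood counts, coagulation, pregnancy test, chromogranin A and urinary 5-HIAA. So 3 of the 6 TLS analytes have no scheduled value at any visit.

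**Step 2. What the schedule can establish.** At least three criteria are needed. The row can be read as six separate items, or as four items with creatinine, uric acid and phosphate sharing one. On either reading the CMP can show at most three criteria: creatinine, potassium and calcium. All three must therefore meet their thresholds.

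**Step 3. A case that meets the definition but cannot be shown.** Take potassium up 30%, calcium down 20%, LDH doubled and creatinine unchanged.

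- Criteria met: potassium + calcium + LDH = 3, on either reading. The definition is satisfied.
- Criteria that can be shown without an LDH baseline: potassium + calcium = 2. The definition is not established.
- Renal rule (Table 5): with age and weight unchanged, Cockcroft-Gault clearance is proportional to 1/creatinine, so the fall is 1 − 1/1 = 0%. Section 3.1 names that formula; its use in Table 5 is assumed. A 0% fall lies in the lowest band (below 25%), where action is left to the investigator. The holds start at a 25% fall.
- The last row of Table 4 could still require a hold, but only for another non-hematologic toxicity that is judged related to carfilzomib and is Grade 3 or higher.

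In this case no rule other than that last row requires drug to be held.

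**Step 4. Size of the correction.** Three analytes at four time points (baseline, Cycle 1 Day 8, Cycle 1 Day 15, Cycle 2 Day 1) give 3 × 4 = 12 results per patient. For 62 patients that is 12 × 62 = 744, if all enrol and all reach Cycle 2 Day 1.

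**The case against.** The strongest reply is that investigators are not confined to the schedule. The sentence on Cycle 2 hydration names both the analytes and the day, which prompts a site to test. It also has a second arm, for patients considered still at risk, that needs no result. Cycle 1 hydration is mandatory, and later hydration may be given as needed. TLS can be declared from the CMP alone when its three markers all move. Eligibility is limited to well-to-moderately differentiated or low-grade tumors, and Section 1.1 describes gastrointestinal carcinoids as generally slow-growing, so TLS may be uncommon.

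Most of this stands for hydration: the gap leaves the named trigger to each site, but it does not leave patients without access to fluids. It does not answer the TLS point, because a test ordered on suspicion cannot supply a missing baseline.

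Two stronger readings go too far.

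- **A restart-dose effect.** A reader might infer that the missing baseline moves patients from the TLS row (restart at 56 mg/m2) to Table 5 (restart at 45 mg/m2 if the event is attributed to carfilzomib). The documents do not support this. TLS and renal dysfunction are parallel rows of Table 4, and nothing says which governs when both apply. Section 6 says only that adjustment follows the organ system with the greatest toxicity. If creatinine rises by 50%, Table 5 applies whether or not LDH has a baseline. That is a separate question of precedence, and adding assays does not settle it. A contrast in release rules is also unsafe: footnote a of Table 4 asks for resolution to Grade 1 or better, and its scope is unclear in the available text.
- **A miss rate.** Read as six items, 20 + 15 + 6 + 1 = 42 combinations contain at least three changes. Only 2 × 2 × 2 = 8 of them include creatinine, potassium and calcium together, which leaves 34. But 34 of 42 counts patterns that are not equally likely, so it says nothing about how often TLS would be missed.

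**Conclusion.** The omission is real and should be corrected. Half of the analytes in the TLS definition (3 of 6) have no protocol-required baseline for any patient. Under exact adherence to the schedule, TLS can be established only when creatinine, potassium and calcium all meet their thresholds. The case in Step 3 shows a qualifying pattern that cannot be demonstrated and for which Table 5 requires no hold. The Cycle 2 hydration trigger is affected less, because judgement offers another route.

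The conclusion assumes that sites do only what is scheduled. A site that adds LDH, uric acid and phosphate at baseline by local habit does not have the problem, but the protocol does not ask for this. No restart-dose difference is claimed. No count of affected patients is given, because the documents contain no TLS frequency. The two-stage response-rate design in Section 10.2 is unaffected.

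**What to change.** 1. In Section 7.2 and the baseline column of Appendix D, add serum LDH, uric acid and phosphate, in the same 7-day window as the CMP.
2. In Section 7.3.1 and Appendix D, add the same three with the CMP draws on Cycle 1 Days 8 and 15 and at Cycle 2 Day 1, using the existing 72-hour pre-dose window. The Cycle 2 Day 1 result is then available for the hydration decision. The Cycle 1 draws cover the period when hydration is mandatory, and the Day 15 draw follows the step up to 56 mg/m2 on Days 8 and 9.
3. In the TLS row of Table 4, state that changes are measured from the baseline value.

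Other testing can stay at the investigator's discretion when TLS is suspected; it will still be needed for changes that arise between draws.

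The cost is up to 12 assay results per patient on blood already drawn (at most 744 in all), with no extra visit. Section 15.1 lists added tests among the changes that need amendment approval from the IRB and/or the FDA or other authorities, so these edits need a protocol amendment and could be combined with the next one.

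### Table 4 gives two incompatible rules for Grade 3 neuropathy: the row and footnote a differ on when to hold, when to restart and who leaves the study

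*Combined protocol and SAP*

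**What the plan says.** Table 4 in Section 6.2 is titled "Carfilzomib Dose Reductions for Grade 3 or 4 Non-Hematologic Toxicities". One of its neuropathy rows is triggered by "Grade 2 treatment emergent neuropathy with pain or Grade 3 neuropathy". The action is "Continue to dose. If neuropathy persists for more than two weeks hold carfilzomib until resolved to" a level given as at or below "Grade 2 without pain. Then restart at 1 dose decrement". Grade 4 neuropathy has its own line (discontinue) and is not at issue.

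The row for other carfilzomib-related toxicity of Grade 3 or higher holds the dose until at or below "Grade 1 or baseline. Restart at 1 dose decrement".

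Footnote a to the table says: "Carfilzomib should be held until toxicity resolves to" Grade 1 or lower. It goes on: "Patients who develop irreversible Grade 3/4 non-hematologic toxicity, or toxicity that does not resolve to" Grade 1 or lower "within 3 weeks, should be removed from the study". It names no row and states no exception. It does not say whether the 3 weeks run from onset or from the hold.

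Section 6 separately discontinues any patient whose toxicity-related delay exceeds 21 days from the intended day of the next scheduled dose. The only exception to a 3-week limit, by agreement of the treating physician and the Study Chair, is footnote c to Table 3, the hematologic table.

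**The concern.** The row and the footnote appear in one table and can apply to the same event. If both apply, they disagree on three things: whether dosing continues at first, which grade permits restart, and whether a patient left with painless Grade 2 neuropathy stays in the trial. Two sites could each follow the printed text and do opposite things. What is at stake is whether a patient with a Grade 3 event receives more drug, and whether that patient is kept on or removed. Differences between sites would also make safety exposure harder to interpret.

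**Working it through.** The plan states no figure to reproduce here. The check sets the texts side by side and follows a patient through the schedule.

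**Side by side, Grade 3 neuropathy (Table 4)**

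| Question | Neuropathy row | Footnote a |
|---|---|---|
| Hold when? | Only after more than 2 weeks | At once |
| Restart at? | Grade 2 or lower, no pain, one level lower | Grade 1 or lower |
| Removal? | None stated | Not at Grade 1 or lower within 3 weeks |

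**Doses before a hold.** Inputs: dosing days 1, 2, 8, 9, 15 and 16 of each 28-day cycle (Table 1) and the row's two-week limit. Suppose Grade 3 neuropathy is found on Cycle 2 Day 1 before dosing. Two weeks later is Day 1 + 14 = Day 15, and Day 16 is the first dosing day past the limit. The row therefore allows Days 1, 2, 8, 9 and 15, which is 5 of the cycle's 6 doses (at 56 mg/m² if there was no earlier reduction). The footnote allows 0.

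**After the hold.** Count onset as day 0. Under the row, the hold begins just after day 14. Suppose that on day 21 the neuropathy is Grade 2 without pain and stays there.

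- If the footnote's clock starts at onset, 3 weeks end on day 21. The row says restart and the footnote says remove.
- If the clock starts at the hold, 3 weeks end at about day 14 + 21 = 35. On day 21 the row says restart and the footnote says keep holding. At about day 35 the footnote says remove.

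The conflict is present with either clock.

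**Does Section 6 settle it?** It sets no recovery grade, and its 21-day limit depends on which hold rule was followed. Under the row, the first missed dose is Day 16 (day 15 from onset), so the limit falls at 15 + 21 = day 36. A restart at the next cycle's Day 1 (day 28) is a delay of 28 − 15 = 13 days and is allowed. Under the footnote, the first missed dose is on day 0 and the limit falls on day 21. Section 6 therefore carries the disagreement forward.

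**The row for other related toxicity.** With a baseline of Grade 0 or 1, return to baseline is also return to Grade 1 or lower, so row and footnote agree on the restart grade. With a baseline of Grade 2 that rises to Grade 3 and falls back to Grade 2, the row permits restart. The footnote does not, and after 3 weeks at Grade 2 it calls for removal. The eligibility criteria in Sections 3.1 and 3.2 set no general cap on the grade of pre-existing non-hematologic conditions, so such patients can enter.

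**The case against.** The strongest objection concerns the reach of footnote a. In the machine-read text of the PDF, no marker for it is visible in the title or in any row, and it may have been lost in conversion. If the original ties it only to the row for other related toxicity, whose wording it echoes, the neuropathy conflict disappears and only the baseline case remains. This stands as a limit on certainty. Against it, the footnote speaks of non-hematologic toxicity without restriction, and footnote b, equally unmarked, plainly covers the whole table.

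A second objection is that the footnote may be a default behind the specific rows. Herpes, infection, heart failure and renal dysfunction all have their own end-points, and a note that overrode every row would displace most of them. That is a sensible reading, but no sentence says so. The neuropathy row also has no removal term of its own to displace the footnote's. The same point counts against a reader who infers that every row of Table 4 is contradicted: the documents do not establish that the footnote is meant to override them.

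Third, the Grade 2-with-pain trigger is arguably outside a table titled for Grades 3 and 4. That is fair, and the point rests on Grade 3.

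Fourth, a reader might infer a distorted response rate, because scans come only every 3 cycles and response needs confirmation. The documents do not support this. CT is scheduled at the end of treatment (Section 7.5) and then every 3 months until progression for patients who stop without it (Section 7.6.1). Section 1.3.2 also reports that carfilzomib did not appear to cause clinically meaningful neuropathy in myeloma studies, so few patients may be affected.

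Finally, the footnote says patients should be removed, which is weaker than an absolute requirement.

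**Conclusion.** The inconsistency is real for Grade 3 neuropathy. Read as printed, Table 4 supports opposite hold, restart and removal actions for one event. In the worked case the difference is up to 5 doses against none, followed by restart against continued hold and removal. This assumes that footnote a reaches the neuropathy row, which its general wording supports but no visible marker confirms. It also assumes that the event is known before the Day 1 dose. The conflict in the row for other related toxicity is narrower and needs a baseline grade above 1. The documents do not allow the number of affected patients to be estimated, and no consequence for the primary endpoint is shown. The matter deserves correction because it governs further drug exposure after a Grade 3 toxicity and the remedy is small. No view is taken on which rule is clinically right.

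**What to change.** Reconcile footnote a with the rows of Table 4. State which rows it governs, place its marker accordingly, and say whether it overrides a row's own terms or applies only where a row is silent. Each event should end up with one hold trigger, one restart grade (with or without the baseline allowance) and one removal rule. Define whether the 3 weeks run from onset or from the hold, and how that limit relates to the 21 days in Section 6. The sponsor's clinical team must choose the rule.

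The cost is a wording amendment to Table 4 through the route in Section 15.1. It needs no new procedures and no change to the sample size or analysis.
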